2.2.2 Benefit Assessment

To date, no treatment of COVID-19 has demonstrated clinical efficacy. Patients and their physicians are critically in need for treatments that decrease the risk of severe levels of disease, particularly the rate of intubation or other ventilatory support as they significantly lead to fatal outcomes. Considering the current pandemic, even a limited improvement in the rate of progression to severe stage of the disease would provide sizable benefits for patients and society.

Nitric Oxide is already marketed (e.g., INOmax[®], NOXIVENT[™], etc) in the United States (US) and other countries as a gas for continuous use in preterm and near-term (>34 weeks gestation) neonates with hypoxic respiratory failure associated with clinical or echocardiographic evidence of pulmonary hypertension in conjunction with ventilatory support and other appropriate agents.

It is well tolerated, although under continuous use, a small number of cases of methemoglobinemia have been reported (NOXIVENT™ FDA Prescribing Information).

Nitric oxide has been shown in vitro to inhibit the replication cycle of severe acute respiratory syndrome coronavirus (Akerström S et al, 2005). In addition, NO is a naturally occurring and potent antimicrobial agent in the human body, which is active against viruses, bacteria, fungus, and yeasts (Fang, 1997). In particular, NO inhibits replication in vitro in a number of respiratory viruses including influenza A and B (Rimmelzwaan et al, 1999, Regev-Shoshani et al, 2013), human rhinovirus (Sanders et al, 1998), and respiratory syncytial virus (Ali-Ahmad D et al, 2003).

The ability of RESP301 to have a marked antibacterial action is highly relevant in the context of treating patients with SARS-CoV-2 infection since superimposed bacterial infection is a critical factor and a major cause of morbidity and mortality. RESP301 would restore and replenish the NO deficiency in patients who have succumbed to SARS-CoV-2 infection. RESP301 also has key advantages over inhaled NO gas, as discussed in Section 2.1.

A vibrating mesh nebulizer is advised for administration of RESP301. Amongst the suitable nebulizers, the device chosen for the study is a commercially available, CE-marked vibrating mesh device that delivers a mist of fine droplets in the size range required for pulmonary deposition (Mass Median Aerodynamic Diameter $< 5 \mu\text{m}$). This has been shown to be ideally suited for penetration deep into the alveolar spaces of the lung. As with all nebulizers in clinical use, there is a residual amount of drug that remains in the nebulizer so that not the full amount of drug is administered. The device operates continuously once initiated and automatically switch off once the medication has been delivered. The device may be used in pediatric and adult populations, as permitted by the prescribed medication, and is suitable for use in home environments or hospital/clinic settings.

As testing inefficient product would distract sites from participating in other research efforts, two interim analysis for futility purpose have been planned.

2.2.3 Overall Benefit: Risk Conclusion

Taking into account the measures taken to minimize risk to participants in this first-in-man study, the potential risks identified in association with RESP301 are justified by the anticipated benefits that may be afforded to participants with COVID-19.

3 Objectives and Endpoints

Table 3-1 Objectives and Endpoints

Objectives	Endpoints
Primary	

 • To evaluate efficacy of RESP301 in preventing progression of hospitalized COVID-19 participants at level 4 in the modified World Health Organization (WHO) ordinal scale into levels >4 	
 • Proportion of participants who progress to level >4 of modified WHO ordinal scale due to COVID-19 by Day 14
Key Secondary	

 • To assess the effect of RESP301 as measured by room air SpO₂ 	
 • Change in room air SpO₂ from baseline over time

 • To assess the effect of RESP301 as measured by the National Early Warning Score (NEWS) 2 symptom score 	
 • Change in NEWS 2 symptom score from baseline over time

 • To assess the treatment response on clinical status 	
 • Change from baseline on the modified WHO ordinal scale at each visit up to Day 28
	
 • Time to improvement to a lower level (<4) of modified WHO ordinal scale
	
 • Time to progression to a higher level (>4) of modified WHO ordinal scale
Additional Secondary	

 • To assess the treatment response on clinical status 	
 • Time to hospital discharge
	
 • Incidence of mortality by Day 28
Safety	

 • To assess the overall safety profile of RESP301 in COVID-19 participants 	
 • Clinical safety laboratory measurements
	
 • Physical examinations
	
 • Vital signs
	
 • Concomitant medications
	
 • Counts and cumulative incidence of: 
 ○ Adverse events (AEs) ○ Serious adverse events (SAEs) ○ Severe AEs

Objectives	Endpoints

To assess the ability of participants to tolerate nebulization	
Incidence of participants unable to tolerate nebulization due to:
Reduction in SpO₂ to < 90%, unless well clinically tolerated according to Investigator's opinionOther clinical signs of intolerance according to Investigator's opinionIncidence of clinical bronchial hyper-responsiveness related to nebulization
Exploratory	

CCI	
CCI

4 Study Design

4.1 Overall Design

This is an open-label, randomized, multicenter, parallel group, concurrent, controlled study in hospitalized participants with COVID-19 requiring supplemental oxygen (WHO ordinary scale level 4) using a sequential adaptive design to evaluate the efficacy and safety of RESP301 added to standard of care (SOC). Approximately 300 adult (male and female) participants will be consented and randomized 2:1 to the Investigational arm or the Control arm. Participants randomized to the Investigational arm will receive inhaled RESP301 (6 mL) administered using a vibrating mesh nebulizer TID for up to 10 days in addition to the standard of care (SOC) while participants in the Control arm will receive SOC alone.

The study will be divided into the following periods:

- Screening period: starts up to 2 days (48 hours) prior to and extends up to the day of treatment initiation (Day 1); Days -2, -1 and 1
- Intervention period: up to 10 days; Day 1 to Day 10
- Efficacy follow-up: Day 14 and Day 28 (± 2 days)
- Safety follow-up: 28 days after treatment initiation; with the participant being contacted by phone call, if not still hospitalized, on Day 28 (± 2 days)

After screening, eligible participants will be randomized to either RESP301+SOC or SOC alone on Day 1, and the study treatment will be initiated as applicable (Table 1-1). Screening and randomization may happen on the same day (Day 1).

An individual administration of study intervention will be stopped, and supplemental oxygen resumed, if threshold limits of SpO₂ 89% or heart rate 120 beats/min (or as indicated by the Investigator) are exceeded (see Section 4.2 and Section 8.1.2). However, the participant may continue with subsequent doses if the Investigator judges that the benefit / risk ratio remains positive. In this case, the instruction to continue should be duly recorded in the participant's hospital file and the subsequent nebulization should be closely monitored. Inhalation of study intervention should be completed within 20 minutes. A staggered dosing approach will be used for the first 10 participants (up to the first Independent Data Monitoring Committee [IDMC] safety review) to monitor tolerability and response to RESP301 (see Sections 6.1 and 9.6).

The study treatment will be permanently discontinued prior to 10 days if the participant:

- Improves to level 1 or 2 of the modified WHO ordinal scale;
- Progresses to a level > 4 of the modified WHO ordinal scale;
- Experiences an event that requires permanent discontinuation as described in Section 7.1.

In the above cases, participants will be considered as ongoing in the study until the final Safety follow-up phone call (Day 28). Participants will be withdrawn from the study prior to Day 10 (Early withdrawal) only if they withdraw consent.

The total study duration for a participant from screening to last follow up will be up to 30 days (±2 days).

Participants will be stratified by country and presence of risk factor(s) for severe outcomes of COVID-19, based on comorbidities and age, as detailed in Section 6.3.

Two interim analyses are planned (see Section 9.5 for details).

An IDMC will be responsible for closely reviewing the safety and efficacy data from the interim analyses and for providing their recommendations on continuation of the study. The IDMC will meet after 10, 20, 60 and 150 participants have completed the study (see Sections 9.5 and 9.6).

4.2 Scientific Rationale for Study Design

NO is a naturally occurring and potent antimicrobial agent in the human body which has been shown in vitro to inhibit replication of severe acute respiratory syndrome coronavirus

(Akerström S et al, 2005), including SARS-CoV2, and other respiratory viruses. NO as an inhaled gas is already marketed in the US and other countries (see Section 2.2.2) but has disadvantages over NO produced locally in the oropharynx or lung airways (lengthy treatment requiring NO canisters, the inhaled NO is expelled in exhalation, the NO gas oxidizes in air to form toxic NO₂ which is a potential lung irritant and a contaminant in the patient's environment, and the half-life of NO in air is short).

RESP301 has potential advantages over inhaled NO gas:

- RESP301 demonstrates powerful evidence in vitro as a broad-spectrum anti-microbial;
- Treatment is quick, easy and portable using a standard handheld nebulizer;
- The formulation is nebulized and forms a fine particle mist that settles on the lung surface, at the point of infection, and is therefore a more targeted approach;
- NO production continues in-situ post treatment;
- Because of the design of the formulation, production of NO₂ is negligible by virtue of the NO₂ being rapidly converted to a NO donor species.

In this study, the effect of RESP301 as an add on treatment to SOC will be evaluated for its efficacy in reducing rate of progression to a more severe level of COVID-19 and for safety by comparison with SOC alone in hospitalized COVID-19 patients. A sequential adaptive design was chosen in order to assess futility and sample size after interim analyses (see Section 9.5). The study design was developed in accordance with the latest WHO and regional regulatory agencies guidelines.

Several risks factors for severe or fatal outcomes have been reported (Bialek et al, 2020; Huang et al, 2020; Novel Coronavirus Pneumonia Emergency Response Epidemiology Team, 2020; Rong-Hui et al, 2020; Zhou et al, 2020). To minimize bias, the results will be stratified according to the known risk factors as described in Section 6.3.

In this study, measures will be in place to trigger discontinuation of study intervention at a SpO₂ limit pre-agreed at the site (see Section 8.1.2). There is no critical level of oxygen saturation below which tissue hypoxia occurs due to the large number of variables that contribute to hypoxia at the tissue and cellular level (temperature, pH, tissue blood flow). As a result, there is no consensus about what constitutes normal and abnormal oximetry (ATS/ACCP, 2003). To support and guide the team in charge of study intervention administration, a default value of SpO₂=89% and heart rate (120 beats/min) has been proposed as a suitable limit of tolerance. However, for the reason stated above, this limit can be overruled by the Investigator in either direction.

Newly released guidelines for ongoing clinical trials during the COVID-19 pandemic have emphasized the need to reduce the burden on sites and clinical trial personnel/investigators whether they be administrative, site visit, or other burdens (ACRO, 2020; EMA, 2020; HRS, 2020). Thus, without blinding and a placebo, along with minimal procedures, the additional burden on clinical staff has been reduced as much as possible.

4.3 Justification for Dose

Studies with nebulized sodium nitrite (AIR001) in healthy subjects and in patients have shown that inhaled nitrite produces dose proportional plasma pharmacokinetic without accumulation following repeated administration, with low systemic blood levels of nitrite and methemoglobin (<3%). Inhaled nitrite at doses up to 90 mg TID displayed a good safety profile and is well tolerated (Rix et al, 2015; Parsley et al, 2013; Simon et al, 2016).

In this study, 6.0 mL RESP301 (delivered dose 62 mg) will be administered via a vibrating mesh nebulizer, TID with at least 6 hours between each dose. Each 6.0 mL dose for nebulization contains the masses described in Table 6-2.

4.4 End of Study Definition

A participant is considered to have completed the study if he/she has completed the Treatment Period and the Follow-up Period (through the Day 28 EoS Follow-up). End of the study is defined as the last participant's last visit or follow up call.

5 Study Population

Prospective approval of protocol deviations to recruitment and enrollment criteria, also known as protocol waivers or exemptions, is not permitted.

The study population will consist of male and female COVID-19 patients, including pregnant women and women of child bearing potential. Participants must be able to provide written consent and meet all the inclusion criteria and none of the exclusion criteria.

5.1 Study Rationale

This is an open-label, randomized, multicenter, parallel group, concurrent, controlled study using a sequential adaptive design to evaluate the efficacy and safety of RESP301 plus SOC versus SOC alone in hospitalized patients with COVID-19 requiring supplemental oxygen (WHO level 4).

Each constituent (see Section 6.2) of RESP301 is used as SOC for various conditions. Product application is straightforward, requiring a few minutes of inhalation using a standard nebulizer. RESP301 is likely to be beneficial in treating patients with COVID-19 who are not receiving ventilation but are using supplementary oxygen in order to maintain a safe level of SpO₂.

Considering the well-established and global use of NO and the device, and the current public health emergency resulting from the COVID-19 pandemic, a Phase2/3 study of RESP301 is considered reasonable in order to generate efficacy data in patients infected with COVID-19.

5.2 Inclusion Criteria

Participants are eligible to be included in the study only if all of the following criteria apply:

Age

1. Participant is ≥ 18 years of age, at the time of signing the informed consent.

Type of Participant and Disease Characteristics

2. Participant has laboratory-confirmed SARS-CoV-2 infection as determined by reverse transcriptase polymerase chain reaction (RT-PCR) or other approved clinical testing prior to randomization.
3. Participant is hospitalized in relation to COVID-19, requiring supplemental oxygen to maintain SpO₂ at a safe level (WHO level 4).

Sex

4. Participant is male or female. All females of childbearing potential, including pregnant females, must consent to urine pregnancy testing at screening to be eligible for the study. (Females who are not of childbearing potential do not need to undergo a pregnancy test at screening).

Informed Consent

5. Participant is capable of giving signed informed consent as described in Appendix 1 which includes compliance with the requirements and restrictions listed in the informed consent form (ICF) and in this protocol.

5.3 Exclusion Criteria

Participants are excluded from the study if any of the following criteria apply:

Medical Conditions

1. Rapidly deteriorating or likely to require escalation to high flow oxygen, invasive or non-invasive ventilatory support within 24 hours according to Investigator's opinion.
2. Unable to safely receive a nebulized treatment for approximately 4 minutes according to Investigator's opinion.
3. Unable to receive or considered ineligible for invasive or non-invasive ventilatory support.
4. History of methemoglobinemia.
5. Uncontrolled asthma or history of severe bronchospasm.
6. Severe (requiring baseline oxygen therapy > 12 h/day prehospitalization) chronic respiratory disease (e.g., known COPD, pulmonary arterial hypertension, idiopathic pulmonary fibrosis, interstitial lung disease).
7. Suspected or confirmed untreated, active tuberculosis.
8. Severely immune-compromised participants in Investigator's opinion.
9. Recent (within 3 months) active coronary artery disease or decompensated heart failure (New York Heart Association class 3-4).
10. Presence of tracheostomy.

Prior/Concomitant Therapy

11. Chronic (≥ 4 weeks) use of corticosteroids > 10 mg/day of prednisone or equivalent within 4 weeks of randomization.

Prior/Concurrent Clinical Study Experience

12. Participation in other clinical investigations utilizing investigational treatment or within 30 days / 5 half-lives whichever is longer.

Diagnostic Assessments

13. Clinically significant abnormalities in clinical chemistry or hematology at screening, defined as:

- Platelet count <50,000 mm³
- Alanine aminotransferase or aspartate aminotransferase >5 × upper limit of normal (ULN).
- Estimated glomerular filtration rate <30 mL/min/1.73 m² (modification of diet in renal disease formula) or requiring hemofiltration or dialysis.

Other Exclusions

14. Anticipated transfer to another hospital which is not a study site during the treatment period.
15. Allergy to any of the components of the study intervention.

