5.3 Exclusion Criteria

Participants are excluded from the study if any of the following criteria apply:

Medical Conditions

1. Rapidly deteriorating or likely to require escalation to high flow oxygen, invasive or non-invasive ventilatory support within 24 hours according to Investigator's opinion.
2. Unable to safely receive a nebulized treatment while on room air for approximately 4 minutes according to Investigator's opinion.

3. Unable to receive or considered ineligible for invasive or non-invasive ventilatory support.
4. History of methemoglobinemia.
5. Uncontrolled asthma or history of severe bronchospasm.
6. Severe (requiring baseline oxygen therapy > 12 h/day prehospitalization) chronic respiratory disease (e.g., known COPD, pulmonary arterial hypertension, idiopathic pulmonary fibrosis, interstitial lung disease).
7. Suspected or confirmed untreated, active tuberculosis.
8. Severely immune-compromised participants in Investigator's opinion.
9. Recent (within 3 months) active coronary artery disease or decompensated heart failure (New York Heart Association class 3-4).
10. Presence of tracheostomy.

Prior/Concomitant Therapy

11. Chronic (≥ 4 weeks) use of corticosteroids >10 mg/day of prednisone or equivalent within 4 weeks of randomization.

Prior/Concurrent Clinical Study Experience

12. Participation in other clinical investigations utilizing investigational treatment or within 30 days / 5 half-lives whichever is longer.

Diagnostic Assessments

13. Clinically significant abnormalities in clinical chemistry or hematology at screening, defined as:
 - Platelet count <50,000 mm³
 - Alanine aminotransferase or aspartate aminotransferase >5 \times upper limit of normal (ULN).
 - Estimated glomerular filtration rate <30 mL/min/1.73 m² (modification of diet in renal disease formula) or requiring hemofiltration or dialysis.

Other Exclusions

14. Anticipated transfer to another hospital which is not a study site during the treatment period.
15. Allergy to any of the components of the study intervention.

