AE/SAE review	X	X	X	X	X	X	X	
Concomitant medication review	X	X	X	X	X	X	X	
Oxygen / respiratory assessment ⁷	X	X	X	X				
SpO ₂ on room air (after at least 1 minute) prior to study intervention administration and immediately at the end of nebulization ⁶		X	X	X				See Section 8.1.2
Modified WHO ordinal scale	X	X	X	X		X	X	See Section 8.1.1

Procedure	Screening (up to 48 hours before Day 1 ¹)	Intervention Period			Early withdrawal	Efficacy follow-up (Day 14) ² (± 2 days)	EoS efficacy and safety follow-up (Day 28) ² (± 2 days)	Notes
		Day 1 ¹	Daily while hospitalized	Day 10 / hospital discharge				
NEWS 2 assessment ⁷		X	X	X				Prior to study intervention in the morning. See Section 8.1.3

Abbreviations: AE=adverse event; aPTT= activated partial thromboplastin time; CBC=complete blood count; Chem 7=blood chemistry panel (sodium, potassium, chloride, bicarbonate/CO₂, blood urea nitrogen, creatinine, glucose); CV=cardiovascular; ECG=electrocardiogram; LFTs=liver function tests; mHb=methemoglobin; PT/INR=prothrombin time/international normalized ratio; RT-PCR=reverse transcription-polymerase chain reaction; SAE=serious adverse event; TID=three times daily.

1. Screening and randomization may be on the same day, providing all eligibility criteria are met.
2. For participants who are already discharged at either the Day 14 or Day 28 (EoS) follow-up, there will be a phone call to check AEs/SAEs, concomitant medications, and modified WHO ordinal scale. At EoS, safety laboratory tests (nitrite and mHb only) and weight will be collected for participants in hospital only.
3. COVID-19 infection must be confirmed and documented in chart with a positive result on a validated test.
4. At Screening: CBC, chem 7, mHb, LFTs, coagulation (PT/INR, aPTT).
On Day 1, Day 3, Day 7 and Day 10, or early withdrawal: CBC and chem 7 (per SOC).
On Day 28: nitrite and mHb (participants in hospital at EoS only).
5. Vital signs: temperature, heart rate, blood pressure, respiratory rate. Vital signs to be repeated as per SOC during treatment period.
6. Study intervention comprises the following procedures which are to be done in order and as quickly as possible:
 - a. Recording of oxygen flow level including mode (nasal cannula, mask)
 - b. Recording of SpO₂ and heart rate
 - c. Discontinuation of supplemental oxygen administration *
 - d. Close participant oversight by trained health care professional until SpO₂ is stable on ambient air after one minute at least *

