 - e. Recording of SpO₂ * pre-nebulization on ambient air
 - f. Preparation of the admixture of RESP301*
 - g. Administration of the nebulization via a vibrating mesh nebulizer while monitoring SpO₂ and heart rate (alarms set to 89% and 120 beats / min, or as indicated by the Investigator, for stopping study intervention administration and resuming supplemental oxygen) * If the participant is unable to tolerate nebulization without supplemental oxygen, nasal oxygen may be administered during nebulization.
 - h. Discontinuation of nebulization after 5 minutes or no product left in the device, whichever comes first *
 - i. Recording of SpO₂ * post nebulization on ambient air
 - j. Resuming supplemental oxygen *
 - k. Participant oversight until SpO₂ is stable *
 - l. Recording of SpO₂ *

* for participants on active treatment arm only
7. Immediately before participant is discontinued from oxygen for study intervention administration (*for participants on active treatment arm only*) and assessment of SpO₂ at room air.

2 Introduction

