2.2.1 Risk Assessment

Table 2-1 Risk Assessment

Potential Risk of Clinical Significance	Summary of Data/Rationale for Risk	Mitigation Strategy
Study Intervention RESP301		
Participants may need to be discontinued from supplemental oxygen for	Study treatment is to be administered via a vibrating mesh nebulizer which is designed for oral inhalation.	Participants unable to be safely discontinued from supplemental oxygen will be

Potential Risk of Clinical Significance	Summary of Data/Rationale for Risk	Mitigation Strategy
several minutes to receive nebulized study treatment		
excluded (Exclusion criterion 2)
 
Treatment administration is to be performed as quickly as possible (Section 1.3)
 
Oxygen saturation (SpO₂) and heart rate will be monitored throughout the study intervention administration (Section 1.3)
 
In case of decrease in SpO₂ or clinical signs of intolerance to nebulization, RESP301 treatment may be paused temporarily and supplemental O₂ resumed or the study treatment may be discontinued permanently (see Section 7.1) per Investigator assessment.

Risk of methemoglobinemia	Very low levels are produced but as methemoglobinemia has been reported with continuous NO gas administration, the risk cannot be firmly ruled out	Participants with a history of methemoglobinemia will be excluded (Exclusion criterion 4) and methemoglobin (mHb) is included in safety laboratory tests (Section 1.3)
Risk of clinical bronchial hyper-responsiveness related to nebulization	Excipients in the nebulized RESP301 include mannitol which is a known bronchial	Participants with a known history of moderate or severe bronchial hyperreactivity

Potential Risk of Clinical Significance	Summary of Data/Rationale for Risk	Mitigation Strategy

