8.1.2 Pulse Oximetry

Pulse oximetry measurements will be performed to evaluate SpO₂ as outlined in the SoA (Table 1-1) and in accordance with the site standard operating procedures, on a medical-grade medical device. Measurements will be taken with a probe on fingertip or earlobe and recorded as percent oxygenated hemoglobin. Supplemental oxygen used at the time of assessment and method of oxygen delivery will be collected and documented along with the SpO₂.

Prior to administration of study intervention, supplemental oxygen will be held for at least a minute and SpO₂ checked in order to ensure participant may safely receive the study intervention. For safety reasons, since due to the current pandemic it cannot be guaranteed that study intervention will be consistently administered under direct medical supervision, the study Investigators should provide study personnel who are able to monitor the participant and their SpO₂ and ensure that should it decrease to a threshold, this would trigger immediate discontinuation. By default, unless overruled by the study Investigator, this SpO₂ threshold is set to 89%. This threshold should be entered into the saturation monitoring device to trigger an alarm during nebulization.

FiO₂ will be measured per site standard practice and recorded in the eCRF. The device used to administer oxygen should also be recorded.

8.1.3 National Early Warning Score (NEWS) 2

The NEWS 2 will be measured prior to study intervention in the morning according to the SoA in Table 1-1.

The NEWS is based on a simple aggregate scoring system in which a score is allocated to physiological measurements, already recorded in routine practice, when patients present to, or are being monitored in hospital (RCP, 2012). Six simple physiological parameters form the basis of the scoring system:

1. Respiration rate
2. Oxygen saturation
3. Systolic blood pressure
4. Pulse rate
5. Level of consciousness or new confusion*
6. Temperature

**The patient has new-onset confusion, disorientation and/or agitation, where previously their mental state was normal – this may be subtle. The patient may respond to questions coherently, but there is some confusion, disorientation and/or agitation. This would score 3 or 4 on the Glasgow Coma Scale (rather than the normal 5 for verbal response), and scores 3 on the NEWS system.*

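### Table 2-1 relies on exclusion criterion 2 to keep out patients who cannot safely come off oxygen, but criterion 2 as reworded in Amendment 1 no longer says so

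*Protocol*

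**What the plan says.** All references are to the Amendment 1 text (Version 2.0) unless stated otherwise.

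- **Risk table (Section 2.2.1, Table 2-1).** The first mitigation for the risk of interrupting oxygen begins "Participants unable to be safely discontinued from supplemental oxygen will be" and ends by stating that they are excluded, citing exclusion criterion 2.
- **Criterion 2 (Section 5.3).** "Unable to safely receive a nebulized treatment for approximately 4 minutes according to Investigator's opinion".
- **Criterion 2 in Version 1.0.** "Unable to safely receive a nebulized treatment while on room air for approximately 4 minutes according to Investigator's opinion".
- **Population (Section 5.2, inclusion criterion 3).** "Participant is hospitalized in relation to COVID-19, requiring supplemental oxygen to maintain" a safe SpO2.
- **Oxygen hold before dosing.** In Section 1.3, Table 1-1 footnote 6, oxygen is stopped at step c for the active arm, and step d requires "Close participant oversight by trained health care professional until SpO₂ is stable on ambient air after one minute at least". Section 8.1.2 says "Prior to administration of study intervention, supplemental oxygen will be held for at least a minute". Table 6-1 in Section 6.1 describes an interruption of a few minutes before each inhalation.
- **Room-air SpO2.** The Schedule of Activities has SpO2 taken "on room air (after at least 1 minute) prior to study intervention administration". Change in room-air SpO2 is a key secondary endpoint (Table 3-1).
- **New allowance in Amendment 1 (footnote 6g and Table 6-1).** "If the participant is unable to tolerate nebulization without supplemental oxygen, nasal oxygen may be administered during nebulization".

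**The concern.** The risk assessment names a specific hazard, taking oxygen away from patients who need it, and answers it first with an eligibility rule. The rule it cites does not contain that condition. A site that applies criterion 2 as written, knowing that oxygen may now be given during nebulization, could reasonably enrol a patient who tolerates a nebulizer on nasal oxygen but cannot safely be without oxygen. Table 2-1 says that such a patient is excluded.

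What is at stake is participant safety at the first dose and the accuracy of the benefit-risk statement, in what Section 2.2.3 calls a first-in-man study. Section 5 does not permit waivers of the enrollment criteria, so the wording of each criterion carries weight. A participant found unable to tolerate the hold after randomization also remains in the ITT population (Table 9-1).

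**Working it through.** There is no design figure to reproduce. The check sets the operative sections of one version side by side, with Version 1.0 for comparison.

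| Item | Version 1.0 | Amendment 1 |
|---|---|---|
| Table 2-1 mitigation | excludes those who cannot safely come off oxygen, citing criterion 2 | same |
| Criterion 2 names room air | yes, for about 4 minutes of nebulized treatment | no |
| Oxygen hold before dosing | at least 1 minute | at least 1 minute (footnote 6, Section 8.1.2); a few minutes in Table 6-1 |
| Nasal oxygen during nebulization | not provided for | allowed if needed |

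**Step 1: does the cross-reference hold?** In Version 1.0 it did, because criterion 2 was tied to room air. In Amendment 1 the room-air words are gone and the cross-reference stays.

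**Step 2: does another criterion cover the point?** There are 15 exclusion criteria, so 14 others. The nearest are criterion 1 (rapid deterioration or likely escalation within 24 hours), criterion 3 (not a candidate for ventilatory support) and criterion 6 (chronic respiratory disease with home oxygen for more than 12 hours a day). None concerns tolerating a period off oxygen.

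**Step 3: is the exposure still there?** Yes. All participants need oxygen at entry, and the hold appears in footnote 6c to 6e, Table 6-1 and Section 8.1.2. The nasal-oxygen allowance is limited to the nebulization itself.

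**Step 4: how much time off oxygen?** Minimum hold of 1 minute per dose x 3 doses per day = at least 3 minutes per day for a participant on oxygen. This describes the schedule and is not an estimate of harm. A participant who does not tolerate the hold can have oxygen resumed (Table 6-1) or be permanently discontinued (Section 7.1), so the exposure of concern is the first hold or first few holds.

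**Step 5: does the later recheck close the gap?** The Day 1 entry in the Schedule of Activities reviews the same criteria before the first dose, so it carries the same omission.

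**The case against.** The strongest reply has five parts.

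1. **The text is superseded.** Amendment 2 (Version 3.0) is dated five days after Amendment 1, and its Section 5.3 and Table 2-1 are not shown. This stands as a limit. Its summary of changes lists only methemoglobin edits to both places, which suggests that the mismatch persists. That evidence is weak: the log also mentions minor language changes throughout, and the Amendment 1 log did not list the change to criterion 2 at all.

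2. **The rewording is coherent.** Once nasal oxygen was allowed during nebulization, keeping the room-air words would have excluded patients the amendment meant to admit. Table 2-1 was softened to say that participants may need to come off oxygen. This explains the deletion for the nebulization period but not for the hold, and the same table row still promises exclusion under criterion 2.

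3. **Criterion 2 can be read to include the hold.** Footnote 6 lists oxygen discontinuation among the steps that make up the study intervention, and Section 8.1.2 describes the hold as a check that the participant can safely receive it. An investigator could read the criterion this way. Its wording does not require it.

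4. **The two time periods differ.** The 4 minutes in Version 1.0 attached to nebulization on room air, not to a separately named hold. This is fair: moving from about 4 minutes to none shows that the room-air condition was removed, not that an explicit hold clause was lost.

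5. **The hold is itself supervised.** A trained professional watches until SpO2 is stable, the investigator may resume oxygen instead of dosing, the first administration is under medical supervision (Section 6.2.1), and Section 7.1 provides for discontinuation. These controls do reduce the risk. They act after randomization and mostly once oxygen has been stopped. The 89% alarm is specified for nebulization (Section 8.1.2) and the limit can be overruled in either direction (Section 4.2). Section 8.1.2 also accepts that direct medical supervision cannot always be guaranteed.

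**Conclusion.** The concern holds for the Amendment 1 text: the exclusion promised in Table 2-1 is not stated in criterion 2 or in any other criterion, while the oxygen hold before dosing remains. It should be fixed.

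Its size is limited. The exposure is a monitored hold of at least 1 minute, mainly at the first dose or first few doses. The documents give no figure for how many participants would be affected, and none is assumed. Sample size, power and type I error do not change.

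The conclusion rests on reading criterion 2 as written, and on the Amendment 1 text, the last version shown with its eligibility section. Whether the mismatch survives in Amendment 2 cannot be determined.

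**What to change.** Reword criterion 2 to exclude participants who, in the Investigator's opinion, either

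- cannot safely be off supplemental oxygen for the pre-dose room-air hold (at least 1 minute, until SpO2 is stable), or
- cannot safely receive the nebulized treatment, with nasal oxygen during nebulization if needed.

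Bring the Table 2-1 mitigation into line with this wording. Patients who need nasal oxygen only during nebulization stay eligible, as Amendment 1 intended.

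The cost is one line in Section 5.3 and matching text in Table 2-1, with possibly a few fewer eligible participants; the documents do not allow that number to be estimated. If Version 3.0 already reads this way, no change is needed.
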